12. DATA AND SPECIMEN BANKING*

De-identified data will be stored in the National Library of Medicine (NLM) on clinicaltrials.gov. Results information will be submitted and will not include individual patient data. Following completion of the study, all identifiers will be permanently deleted after the final report to the sponsor has been completed

13. Data Analysis and Management*

INVESTIGATOR STUDY PLAN - REQUIRED

Data will be collected by tablet and email links in REDCap. Our statistician at Yale will manage the data. To evaluate acceptability and use characteristics, we will collect descriptive statistics on satisfaction, helpfulness, and ease of use (SUS and UES) for the Text4Moms system and components (including chat), measured at the intervention (week 8). For engagement, data from the Text4Moms system will be reported showing the percentage of individuals who engage with Text4Moms and read at least 80% of texts and the percentage of individuals who engage with the chat. Qualitative responses from participants will offer further insight into these outcomes.

For efficacy outcomes, total scores on EPDS, GSE and PMS¹¹³ (scales) and the onset of an MDE will be reported using means and standard deviations; frequencies and percentages for the EPDS, GSE and PMS scores will be reported as linear variables. Multiple regression will be used to test for differences in the EPDS, and the GSE and PMS scores between treatment groups at week 8, adjusting for baseline scores. Generalized estimating equations will be used to explore if changes in EPDS, GSE and PMS scores varied over time from baseline to week 4 and week 8. We will also examine whether the percentage of individuals who experience an MDE at week 4 and/or week 8 differed between treatment groups using chi-square tests.

We will test for target engagement by measuring changes in the self-efficacy construct (GSE and PMS) between the 2 groups at 4 and 8 weeks. We will do the same for RDOC constructs measured with IDS-SR items. As an exploratory analysis, we will estimate correlations between EPDS scores and the GSE and PMS scores with treatment. We note power is not sufficient to detect mediating effects.

Sample Size. Leon, [name], & Kraemer state (2011) that “power analyses should not be presented in an application for a pilot study that does not propose inferential results”.¹²⁴ Indeed, pilot studies are not expected to be fully powered. Instead, we based our sample size on accepted practice for pilot studies, the considerable experience of the research team, and practical considerations.¹²⁵ As a pilot study, we are powered at 80% to detect large effect sizes on continuous outcomes ($d > 1.1$) with 20 participants in the Text4Moms group and 10 in the control group and a two-tailed alpha of 0.05. However, we include benchmarks of $d > 0.20$ for the EPDS and possible mediators since this is consistent with the effect size for many digital interventions in the literature.

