5. BACKGROUND*

5.A.1 Significance

Perinatal depression is common, impairing, and preventable. In the United States, ~14% of pregnant individuals experience an incident major or minor depressive episode, with a similar rate occurring postnatally.^{2,3} Depressive disorders always carry a high personal toll. However, during this pivotal time, depression is associated with risk of preterm birth⁴; can negatively affect the dyad through impaired maternal-child attachment⁵⁻⁷; can adversely affect infant development⁸; and decrease breastfeeding initiation/duration.^{9,10} Federal agencies and provider organizations emphasize the need to screen individuals for depression in pregnancy and after delivery.^{11,12} Additionally, the US Preventative Services Task Force (USPSTF) showed compelling evidence that counseling strategies can be deployed to *prevent* perinatal depression (pooled risk reduction (RR)=0.61 [95% CI, 0.47 to 0.78], k=17, n=3094, I²=39%).¹³

INVESTIGATOR STUDY PLAN - REQUIRED

At risk individuals benefit the most from preventative interventions although at-risk determinations vary in the literature. While the USPSTF reviewed preventative strategies for both individuals considered “at risk” and those not necessarily at risk, high risk groups show the greatest reduction in depressive symptoms after engagement in an intervention (RR=0.55; 95% CI, 0.44 to 0.68).¹³ A number of factors constitute risk including a past history of depression, especially perinatal depression¹⁴⁻¹⁸; genetic factors¹⁹⁻²¹; history of sexual abuse, early childhood abuse and intimate partner violence^{22,23}; stress and poor social support^{14,18,24-26}; low socioeconomic status¹⁴; undesired pregnancy²⁷; perinatal complications²⁸; certain demographic characteristics such as adolescence²⁶ and extant subsyndromal depressive symptoms.^{29,30} Measures designed to *predict* who will become depressed³¹⁻³³ do not perform substantially better than questionnaires that include demographic items and query current symptoms, most likely because of collinearity among domains.^{34,35} On the other hand, screening for existing depression is successful. A variety of approaches are used including screening and mood monitoring via mobile applications and text messaging.³⁶⁻³⁹ Systems most commonly use the Edinburgh Postnatal Depression Scale (EPDS)^{38,39} and the Patient Health Questionnaire-9 (PHQ-9)^{36,37} as screeners. The acceptability of tech-based screeners is high.^{37,38}

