- The General Self Efficacy Scale (GSE scale)⁶⁸ has 10 items scored from 1-4 that measures an individual's belief that she can respond to novel or challenging situations. It takes ~2-4 minutes to complete, has a Chronbach's alpha of 0.82-0.93 and in individuals, is a single factor and correlated highly with self esteem and optimism. This is a target of the intervention that is putatively linked with depression risk. We evaluate whether the TMI changes self-efficacy and hence risk of an MDE.
- The Pearlin Mastery Scale (PMS)¹¹³ has 7 items that are scaled 1-4 (1= strongly disagree to 4= strongly agree) with a range of 7-28, and low scores indicating low mastery (Chronbach's alpha=0.78). This is also a target of the intervention and may be associated with lower risk of worsening depression.
- System Usability Scale¹¹⁴ has 10 items and is scored 1-5 (strongly agree to strongly disagree). Scores are summed and multiplied by 2.5. A score of greater than 68 is considered above average. This is a measure of acceptability that bears on ability to implement the system.
- User Engagement Scale – short form¹¹⁵ is a 12 item scale that scores from strongly disagree to strongly agree (1-5). It has 4 subscales with 3 items each. The subscales are Focused Attention; Perceived Usability; Aesthetic Appeal; Endurability. The overall reliability (ω) was 0.88 in formative work; subscales have reliability that is close to this statistic. This is an additional measure of acceptability and hence ability to implement the TMI.

Study Process: After randomization, participants will be sent texts 3-4 times per week (this may change depending upon input from the PGG). Texts will be short and for the TMI, will include video links that reinforce information relevant to IPT. Texts will also be tailored for stage of pregnancy, history of perinatal depression, and possibly other factors such as age depending upon input from the PGG and the EAB. Texts will continue for 8 weeks unless the participant elects to “STOP” texts. They will include a button that will invite individuals to chat with a peer.

INVESTIGATOR STUDY PLAN - REQUIRED

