Control Condition: The control condition will be limited to texts related to pregnancy, nutrition and sleep and will avoid elements that have behavioral therapeutic effects. We will develop a set of texts from openly available information about healthy pregnancy. Although this condition is meant to constitute time and attention control as recommended by an NIH expert panel¹²³, we will include material on recognizing depression and links to ways to attain depression treatment and suicide hotline information.

Peers: We will employ 2-3 individuals as peers; these will be individuals who experienced perinatal depression or were close to someone with perinatal depression. We will recruit from social media, contact providers and the local chapters of PSI. Peers will be encouraged to cluster their texts and will be paid hourly for training and meetings and a modest amount for each text (~\$5). CIAS 3.0 will include a variety of phrases, messages and resources that can be copied and pasted into the chat and thus help peers with messaging about content. Chats will be monitored by the study team. This will ensure the safety of participants and peers and will allow the study team to know if the content is being utilized. Peers will have a safety protocol should a participant experience psychiatric worsening and/or develop suicidal ideation.

Randomization. The 30 participants for the pilot will be randomized in a 2:1 ratio for Text4Moms: Educational control. We acknowledge that the short duration of an R34, and the need to spend at least a year building the system, limits our follow-up period. To collect information about the TMI functionality at various times in pregnancy and after delivery, we will stratify enrollment to 15 individuals who are before 24 completed weeks of pregnancy and 15 who are after 24 completed weeks of pregnancy. This will allow us to pilot the TMI in all phases of pregnancy and the postpartum period since the TMI will endure for 8 weeks. The statistician will generate an allocation sequence for a random-permuted block randomization using identification numbers. After a participant meets criteria and provides consent, the statistician will email the research assistant (RA) the randomization condition. The RA will have no prior knowledge of the randomization sequence. Randomization will occur by the toss of a coin and will not rely on factors other than the stratification.

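### The week-8 regression leaves out the gestation stratum, the only factor randomisation relies on; adding it is a cheap improvement, and the exploratory GEE should name a treatment-by-visit term

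*Combined protocol and SAP*

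**What the plan says.** Section 11 (Randomization) sets the gestation split: "we will stratify enrollment to 15 individuals who are before 24 completed weeks of pregnancy and 15 who are after 24 completed weeks". Its stated purpose is "To collect information about the TMI functionality at various times in pregnancy and after delivery". On the mechanism, the same paragraph says both "The statistician will generate an allocation sequence for a random-permuted block randomization using identification numbers" and "Randomization will occur by the toss of a coin and will not rely on factors other than the stratification". It does not say whether the blocks are built separately within each gestation group.

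Section 13 (Data Analysis and Management) plans a multiple regression for differences in EPDS and in "GSE and PMS scores between treatment groups at week 8, adjusting for baseline scores". Gestation appears nowhere in that section. It then adds: "Generalized estimating equations will be used to explore if changes in EPDS, GSE and PMS scores varied over time from baseline", at weeks 4 and 8. That sentence names neither a treatment-by-visit term nor a standard-error method. The next paragraph does state that change in self-efficacy will be compared between the two groups at 4 and 8 weeks, without naming a model.

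**The concern.** A factor used to restrict randomisation normally belongs in the analysis model. When blocks balance the arms within strata, variation between strata cannot contribute to the sampling error of the treatment difference. A model without the stratum nevertheless counts that variation as residual noise. The standard error is then too large and the interval too wide.

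Aim 2 is to estimate the direction and size of the effect with only 10 controls, so interval width is a real part of what the pilot delivers. A gestation effect on the week-8 score is possible. Eight weeks after entry the two groups stand on either side of 32 weeks (24 + 8), the later group includes women who have delivered, and "Texts will also be tailored for stage of pregnancy, history of perinatal depression".

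The smaller, second issue is the GEE. It is the only named model that reaches week 4 for the scale scores, and as worded it asks whether scores change over time. H1 and H2 ask whether change differs between arms.

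**Working it through.** **The plan's own figure.** Section 13 (Sample Size) gives 80% power for d > 1.1 with 20 vs 10 and two-sided alpha 0.05. The standard error in SD units is √(1/20 + 1/10) = 0.387, so 1.1/0.387 = 2.84 and normal-approximation power is Φ(2.84 − 1.96) = 81.1%. The noncentral t with 28 df gives 78.3%. The stated figure reproduces and is not in dispute.

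**Inputs.** From the documents: n = 30, 20:10, 15 per gestation group, and baseline score as the only covariate. Assumed, because the documents do not give them: within-stratum correlation of baseline and week-8 scores ρ = 0.5, and a gestation effect δ of 0, 0.3, 0.5 or 0.8 SD.

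**Closed form, blocks within stratum.** With the stratum in the model the residual variance is 1 − ρ² = 0.75. A 15/15 indicator has variance 0.25.

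- *Gestation shifts week 8 only.* Without the stratum the residual variance is 0.75 + 0.25δ². The interval ratio is about √[(0.75 + 0.25δ²)/0.75]: √(0.8125/0.75) = 1.041 at δ = 0.5, and √(0.91/0.75) = 1.102 at δ = 0.8.
- *Gestation shifts baseline and week 8 equally.* The baseline score already absorbs part of it. What remains is (1 − ρ)²δ² times v, the stratum variance not explained by baseline, where v = 0.25 − (0.25δ)²/(1 + 0.25δ²). At δ = 0.5, v = 0.235 and the ratio is √[(0.75 + 0.0625 × 0.235)/0.75] = 1.010. At δ = 0.8, v = 0.216 and the ratio is √[(0.75 + 0.16 × 0.216)/0.75] = 1.023.

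**Simulation**, which also counts the degree of freedom (27 vs 26). Excess 95% CI width when the stratum is omitted, ρ = 0.5:

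| δ (SD) | Within-stratum blocks, shifts week 8 only | Within-stratum blocks, shifts both equally | One unstratified 20:10 list, shifts week 8 only |
|---|---|---|---|
| 0 | −0.2% | −0.2% | about −2% |
| 0.3 | 1.4% | 0.1% | about −0.5% |
| 0.5 | about 4% | 0.7% | about 2% |
| 0.8 | about 11% | about 2% | about 8% |

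With within-stratum blocks and a week-8-only shift, type I error without the stratum is about 4.1% at 0.5 SD and 3.3% at 0.8 SD, against about 5% with it. The true sampling SD of the estimate is about 0.34 either way, so only the reported standard error is wrong. With the unstratified list, type I error stays at 4.9–5.3%, so the standard error is valid.

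**GEE.** With 2:1 allocation, a time-only coefficient estimates (2/3)Δ_T + (1/3)Δ_C, where Δ_T and Δ_C are the mean changes on Text4Moms and control. The contrast in H1 and H2 is Δ_T − Δ_C. If both arms change by the same amount c, the time coefficient is c and the contrast is 0. The variance method also matters at this size. In simulations of a model with treatment, visit, their interaction, baseline score and stratum (20/10, complete data), an uncorrected sandwich with a normal reference gives type I error of 8.2–8.5%. With a t reference, Mancl–DeRouen gives 4.0–4.2% and Kauermann–Carroll 5.3–5.7%.

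**The case against.** The strongest reply is that the defect depends on two unknowns. First, section 11 speaks of stratifying enrolment in order to see how the system functions at different stages, which fits a recruitment quota as well as stratified allocation. Without within-stratum blocks there is no standard-error error at all. Second, gestation must predict the week-8 score beyond the baseline score. Section 5 reports that about 14% of pregnant individuals "experience an incident major or minor depressive episode, with a similar rate occurring postnatally", so no effect is within range. If gestation shifts both scores alike, baseline adjustment already removes most of it. H1 and H2 are also point benchmarks of d ≥ 0.2, and the point estimate is unbiased.

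All of this stands, and it limits the size of the point. It does not remove the case for the term. The plan itself calls gestation the stratification that randomisation relies on, and leaving it out is nowhere justified. The pilot argument in section 13 concerns sample size, not covariates.

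On the GEE, the reply is that it is exploratory and that the between-group intent is stated in the next paragraph. That is correct: the intent is there, but the week-4 model is not.

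A reader might infer three stronger things. One is that the omission biases the effect or raises the false-positive rate; the week-8 error is in the conservative direction or absent. Another is that intervals will be 4–11% too wide; that needs an effect which appears only after baseline, together with within-stratum blocks. The third is that the GEE will run at 8% type I error; the plan names no standard-error method, so that figure is a reason to name one and not a fault in the text.

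**Conclusion.** The point holds as a free or cheap improvement of minor severity. The week-8 regression omits the one factor that section 11 says randomisation relies on. There is no bias.

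At an assumed baseline correlation of 0.5 and gestation effects of 0–0.8 SD, with blocks within stratum, the interval is 0–2% too wide if gestation acts on both scores equally. It is up to about 4% (0.5 SD) or 11% (0.8 SD) too wide if gestation acts on week 8 only. If allocation is not stratified, the standard error is correct, and adding the term moves the interval from about 2% wider to about 8% narrower.

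The correlation, the size of the effect and whether it is already present at baseline are all assumptions. The one firm textual conflict is permuted blocks against a coin toss, and it decides which case applies. The GEE wording is secondary.

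**What to change.** Section 13, week 8:

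> Week-8 scores will be regressed on treatment, baseline score and gestation stratum (before/after 24 completed weeks) and reported with 95% CIs. This regression is the governing week-8 analysis.

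Section 13, exploratory GEE: include treatment, visit, treatment × visit, baseline score and stratum, with a named small-sample standard-error correction. Use it for the week-4 between-group contrast and as supportive evidence at week 8. No wider redesign of the longitudinal analysis is needed.

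Section 11: reconcile the permuted-block and coin-toss sentences, and state whether the blocks are built within each gestation stratum.

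Cost: wording, plus one degree of freedom. If gestation has no effect, the interval is 0.2% wider with within-stratum blocks and about 2% wider without them. No extra data are needed. The assessment table in section 11 has no row for the mastery scale and marks the QIDS items at baseline only; that is a separate matter, to be settled before the same wording is applied to those measures.

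### Section 13 uses GEE with 20 v 10 participants but names no standard-error type, small-sample correction or arm-by-time term; run in its usual form, its arm-by-time tests would reject a true null about 8% (one contrast) to 10% (joint) of the time

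*Combined protocol and SAP*

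**What the plan says.** Section 11 (Randomization) fixes the size and allocation: "The 30 participants for the pilot will be randomized in a 2:1 ratio for Text4Moms: Educational control". Section 13 (Sample Size) gives the arms and the test level: "with 20 participants in the Text4Moms group and 10 in the control group and a two-tailed alpha of 0.05".

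Section 13 (Data Analysis and Management) contains three statements about analysing EPDS, GSE and PMS between or within arms:

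- A baseline-adjusted regression at one visit: "Multiple regression will be used to test for differences in the EPDS, and the GSE and PMS scores between treatment groups at week 8".
- A longitudinal model, whose sentence also takes in the week-8 visit: "Generalized estimating equations will be used to explore if changes in EPDS, GSE and PMS scores varied over time from baseline to week 4".
- A between-group comparison of change, with no model named: "We will test for target engagement by measuring changes in the self-efficacy construct (GSE and PMS) between the 2 groups at 4 and 8 weeks".

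The GEE sentence gives no working correlation, no choice between robust and model-based standard errors, no reference distribution, no small-sample correction and no arm-by-time term.

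**The concern.** The usual GEE inference takes the sandwich variance and refers the Wald statistic to a normal or chi-square distribution. Both steps are justified when there are many independent participants. Here there are 30, and the control arm has 10. The sandwich is then biased downward, and the reference distribution ignores the few degrees of freedom behind the variance estimate.

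This matters because GEE is the only method named for these scores that reaches week 4. It is therefore the natural vehicle for the planned comparison of GSE and PMS change between arms at 4 and 8 weeks, which is how target engagement (H1 in Section 4) is to be examined. Intervals that are too narrow would overstate how precisely a small pilot has measured the direction and size of effect that Aim 2 sets out to describe.

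**Working it through.** **Inputs from the documents.** 30 randomised 2:1 (Section 11); 20 v 10 and two-sided alpha 0.05 (Section 13, Sample Size); visits at baseline, week 4 and week 8 (Section 13).

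**Assumptions, because the documents give no values.** Identity link, categorical visit, arm-by-visit terms, normal errors, and either complete data or 20% loss.

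**The plan's own figure first.** Section 13 says "we are powered at 80% to detect large effect sizes on continuous outcomes", meaning d above 1.1.

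- Standard error of d = √(1/20 + 1/10) = 0.387.
- 1.1/0.387 = 2.84, and 2.84 − 1.96 = 0.88, so power is about 81.1% by the normal approximation.
- The noncentral t with 28 df gives 78.3%.
- The d for exactly 80% power is 1.085 (normal) or 1.124 (t).

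The stated figure reproduces. The plan states no error rate for the GEE.

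**Why the sandwich is too small.** With complete data and the model above, the GEE arm-by-time contrast is the difference between arms in mean change. Its sandwich variance is SS₁/n₁² + SS₀/n₀², where SS is the within-arm sum of squared deviations of the change scores.

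- Expected value relative to the true variance: (1/20 × 19/20 + 1/10 × 9/10)/(1/20 + 1/10) = 0.1375/0.15 = 0.917.
- Standard error ratio: √0.917 = 0.957.
- Using 1.960 instead of the t value of 2.048 (28 df) multiplies the interval by a further 0.957.
- Together: 0.957 × 0.957 = 0.916, so the interval is about 8% to 9% shorter than the pooled-t interval for the same contrast (8.8% by simulation).

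**Rejection of a true null at nominal 5%** (simulation, at least 200,000 replicates per setting). With complete data the correlation between visits only rescales the change scores and does not alter these rates.

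| Method | 20 v 10, one contrast | 20 v 10, joint 2 df | 16 v 8, one contrast | 16 v 8, joint 2 df |
|---|---|---|---|---|
| Uncorrected robust, normal/chi-square | 7.6% | 10.1% | 8.3% | 11.6% |
| Mancl-DeRouen, normal/chi-square | 5.5% | 7.1% | 5.6% | 7.6% |
| Mancl-DeRouen, t / Hotelling-type F | 4.6% | 4.9% | 4.5% | 4.8% |
| Kauermann-Carroll, t / Hotelling-type F | 5.5% | 6.1% | 5.5% | 6.2% |
| Pooled t-test on change | 5.0% | – | 5.0% | – |

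Coverage of the uncorrected 95% interval at 20 v 10 is 100 − 7.6 = 92.4%.

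**Cross-check with a GEE routine** (exchangeable working correlation, 3,000 replicates per setting, Monte Carlo error about 0.5 point).

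- Robust tests, complete data: 7.2% for one contrast and 9.6% jointly.
- Robust tests, 20% assumed dropout: 7.9% and 11.1%.
- Robust test, linear arm-by-time slope: 8.0%.
- Heavier-tailed or skewed errors, by direct simulation: 7.2% to 7.4% for one contrast.

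**Model-based standard errors in the same routine.**

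- Exchangeable data, so the working correlation is right: 5.6% for one contrast and 5.0% jointly.
- AR(1) data with an exchangeable working correlation, linear slope and 20% dropout: 11.0%, against 8.7% for the robust test.

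**The case against.** The plan does not say that it will use large-sample robust errors. It says nothing, so the 7.6% and 10.1% describe a common default and not a stated method. With model-based errors and a correct working correlation the problem almost disappears. The GEE sentence also contains no arm-by-time test. It speaks of exploring change over time, and the joint 2-df test is supplied here, not by the plan. All of this stands, and the point is worded conditionally for that reason. It does not remove the point: the error rate depends on choices the plan leaves open, model-based errors can do worse than robust ones when the correlation is wrong, and the planned between-group comparison of change at both visits makes an arm-by-time test the likely use.

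A reader might infer that any disagreement between the GEE and the week-8 regression would come from the variance estimator alone. The documents do not support that. The GEE contrast compares change scores, while the regression adjusts for baseline, so the two can disagree with correct variances. In 200,000 null replicates at 20 v 10 and correlation 0.5, the uncorrected GEE was significant and the regression was not in 4.4% of trials. With a correct pooled t-test on change in place of the GEE it was still 2.3%. At correlation 0.7 the figures were 3.9% and 1.8%. About half of the disagreement is due to the different estimators.

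A reader might also infer that the hypotheses are put at risk. H1 and H2 (Section 4) and the benchmarks in Section 13 are effect-size thresholds of 0.2. With complete data, correcting the variance leaves the estimated difference unchanged, and no progression decision is tied to a GEE p-value.

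**Conclusion.** The concern holds as a conditional one. Section 13 leaves the GEE's inference unspecified at a sample size where its ordinary form is not accurate. Under that form, with arm-by-time tested, the excess over 5% is about 2.6 percentage points for one contrast and about 5 points for the joint test. It is somewhat larger with dropout.

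This rests on an uncorrected sandwich with a normal or chi-square reference, an arm-by-visit model, and assumed error distribution and dropout.

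The consequence is modest. The GEE is exploratory, the baseline-adjusted week-8 regression with its usual t-based inference is unaffected, and the 0.2 benchmarks do not use GEE standard errors. It is worth settling before analysis because the remedy is cheap and the inflation is avoidable.

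**What to change.** Amend Section 13 to state that the GEE includes arm, visit (baseline, week 4, week 8) and arm-by-visit, and that inference uses the Mancl-DeRouen bias-corrected variance with a t reference for single contrasts and an F reference (Hotelling-type scaling) for the joint test. Name the working correlation as well. The reference distribution must be part of the change: correcting the variance alone leaves about 7% on the joint test. Kauermann-Carroll is less satisfactory for the joint test, at 6.1% even with the F reference.

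A linear mixed model for repeated measures, fitted by REML with Kenward-Roger degrees of freedom and the same terms, is an acceptable alternative.

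The cost is about one sentence and no extra data. Intervals widen: at 20 v 10 the Mancl-DeRouen t interval for one contrast is about 14% wider than the uncorrected one, and about 4% wider than the pooled-t interval, by simulation. By arithmetic, the expected variance ratio to the truth is (1/19 + 1/9)/0.15 = 1.092, so the standard error ratio is 1.045. Then 1.045/0.957 × 2.048/1.960 = 1.14.

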4. OBJECTIVES*

Aim 1: Draw upon the literature and a User Centered Design approach to collect data from content area experts, caregivers, and individuals with lived experience of perinatal depression, to iteratively develop the Text4Moms tool (tailored text messages, video content, and peer navigator dashboard).

Aim 2: Evaluate preliminary effect direction and magnitude of Text4Moms in a pilot randomized trial (Text4Moms vs educational texts; ratio 2:1) with 30 at-risk pregnant individuals not in an MDE. *Compared to participants randomized to the control condition, those in Text4Moms will:* **H1:** show target engagement through improvement in “self-efficacy” of $\geq d = 0.2$ that can protect against development of an MDE; **H2:** show greater decline in Edinburgh Postnatal Depression Scale (EPDS) scores of $\geq d = 0.2$, and items indicative of RDOC constructs of “loss” and “threat.”¹

Aim 3: Examine implementation outcomes by evaluating the usage, acceptability, and feasibility of Text4Moms and its components: **H3:** Participant ratings will average at least 68 on the System Usability Scale for the Text4Moms system and components. **H4:** >70% of patients will show engagement in Text4Moms by opening $\geq 80\%$ of text messages and clicking on $\geq 30\%$ of links to enhanced content. **H5:** $\geq 30\%$ of mothers will engage with the chat and endorse 4 out of 5 on its utility.

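### H1 and H2 are framed as d of at least 0.2, but Section 13 does not define d, plans no confidence interval, and does not say how 0.2 will be compared with the data

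*Combined protocol and SAP*

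**What the plan says.** Section 4 (Objectives) gives the purpose of Aim 2 as to "Evaluate preliminary effect direction and magnitude of Text4Moms in a pilot randomized trial". Under H1, Text4Moms participants will "show target engagement through improvement in" self-efficacy of d at least 0.2 relative to control. H2 sets the same figure for a greater fall in EPDS score.

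The Sample Size paragraph of Section 13 says that pilots are not expected to be fully powered. It states 80% power for d above 1.1 "with 20 participants in the Text4Moms group and 10 in the control group and a two-tailed alpha of 0.05", and then keeps benchmarks of d above 0.20 "for the EPDS and possible mediators since this is consistent with the effect size for many digital interventions in the literature".

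The analysis text of Section 13 says: "Multiple regression will be used to test for differences in the EPDS, and the GSE and PMS scores between treatment groups at week 8", with adjustment for baseline. It adds means and SDs, exploratory GEE over weeks 4 and 8, chi-square tests for MDE, and a test of target engagement on GSE and PMS at 4 and 8 weeks. It names no standardized effect size, no SD to standardize by, and no confidence interval for any efficacy outcome.

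**The concern.** The hypotheses are written in one quantity and the analysis in another. H1 and H2 turn on the size of d. Section 13 delivers p-values from tests that have little chance of detecting an effect of that size. Nothing connects the two, so after the data are in, someone must decide what d is (week 4 or week 8, adjusted or not, which SD, GSE or PMS) and what it means for d to exceed 0.2.

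An aim about direction and magnitude needs an estimate with its precision. Without one, an observed d a little above 0.2 could be reported as target engagement or symptom benefit although it is well within what chance produces with 30 participants.

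**Working it through.** **Inputs from the documents:** 20 v 10; two-sided alpha 0.05; benchmark d = 0.2; stated 80% power for d above 1.1; regression at week 8 adjusted for baseline. **Assumed:** the baseline to week-8 correlation r, which the documents do not give (0.5 to 0.8 tried), and no dropout unless stated.

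**1. The plan's own figure.** Power at d = 1.1 is 78.3% by the noncentral t (28 df) and 81.1% by the normal approximation. The effect detectable with 80% power is d = 1.12 (t) or 1.09 (normal). The stated figure reproduces.

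**2. Precision of d, unadjusted.**
- SE(d) = sqrt(1/20 + 1/10) = 0.387, nearly twice the benchmark.
- 95% half-width = 1.96 × 0.387 = 0.76 (0.79 with the t quantile).
- An observed 0.2 has an approximate 95% CI of -0.56 to 0.96.

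**3. Power of the planned test at d = 0.2.** The noncentrality is 0.2/0.387 = 0.516. Power is 7.9% (t) or 7.4% (normal). The unadjusted t test reaches significance only when the observed d is about 0.79 (the half-width in step 2). Any d between 0.2 and 0.79 therefore meets the benchmark and fails the test, and the plan does not say which governs.

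**4. Chance of an observed d of at least 0.2 with no true effect, one outcome, unadjusted.** P(Z ≥ 0.2/0.387) = P(Z ≥ 0.516) = 30.3%. With the t distribution it is 30.5%, and with Hedges' correction 30.0%. With 16 v 8 completers (20% dropout, assumed) it is 32.4%.

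**5. The same with the planned baseline adjustment, scaled by the raw SD.** SE = 0.387 × sqrt(1 - r²).

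| r (assumed) | SE | P(observed d ≥ 0.2, no effect) | 95% half-width (normal to t, 27 df) |
|---|---|---|---|
| 0.5 | 0.335 | 27.5% | 0.66 to 0.69 |
| 0.7 | 0.277 | 23.5% | 0.54 to 0.57 |
| 0.8 | 0.232 | 19.5% | 0.46 to 0.48 |

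If the adjusted difference is divided by the residual SD instead, the chance stays near 30%. If d is taken from change scores on the raw SD, as the H2 wording about decline could suggest, it is 30.3% at r = 0.5 and 25.2% at r = 0.7. The choice of definition therefore matters.

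**6. Chance of missing the benchmark when there is an effect.** With a true d of 0.2 it is missed 49.8% of the time, and adjustment leaves this at about half. With a true d of 0.5 it is missed 21.8% of the time unadjusted. At r = 0.7, (0.5 - 0.2)/0.277 = 1.08, which gives about 14%.

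**7. Availability of the data.** The assessment table in Section 11 has EPDS and General Self Efficacy at baseline, 4 and 8 weeks. It has no row for the Pearlin Mastery Scale, although Sections 10, 11 and 13 treat that scale as an outcome.

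**The case against.** The best reply is that this is an openly underpowered pilot, that d = 0.2 is called a benchmark, and that no passage says an observed 0.2 establishes anything. If the significance tests decide H1 and H2, a favourable result under no effect occurs about 2.5% of the time per test, not 30%. Low power, which the sample-size text largely discloses, is then the only problem. Group means and SDs are planned, so a reader could work out a rough d and interval.

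Much of this stands. The documents contain no success rule and no progression rule, so the 20-30% figures hold only if the benchmark is read as a point estimate. That reading is natural, because a test with about 8% power at 0.2 cannot sensibly be the means of judging whether d reaches 0.2, but the plan does not state it.

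The reply does not remove the gap. Disclosing low power does not say how the retained benchmark will be used. A d derived from means and SDs is unadjusted and leaves the time point, the scale and the standardizer open. If the tests are meant to decide, H1 and H2 should not be worded as d of at least 0.2.

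**Conclusion.** The point holds as a gap between hypotheses and analysis. H1 and H2 are expressed as d of at least 0.2, while Section 13 neither defines d, nor plans an interval, nor says how 0.2 is to be read. On the point-estimate reading, an intervention with no effect reaches 0.2 on a given outcome about 30% of the time unadjusted, and roughly 20-28% after baseline adjustment on the raw SD. Even at r = 0.8 the 95% interval around an observed 0.2 runs from about -0.26 to 0.66. The adjusted figures rest on assumed correlations.

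A reader might infer three stronger things that the documents do not support:
- That the trial will declare success, or abandon the intervention, on an observed d. No such rule is written.
- That a flat 30% false-positive rate applies. That figure is for an unadjusted d, and the plan adjusts for baseline.
- That the chance should be compounded over GSE, PMS and EPDS. Nothing says that one scale out of several is enough, and H1 and H2 are separate hypotheses.

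**What to change.** In Section 13, make the baseline-adjusted week-8 between-group difference, and its standardized value, each with a 95% CI, the main Aim 2 result for the EPDS and GSE. Fix the standardizing SD in advance; the pooled baseline SD is one reasonable choice. Add PMS once it has been reconciled with the Section 11 assessment table.

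Pre-specify one scale as the H1 measure. GSE is the one already scheduled at all three time points. Reword H1 and H2 in Section 4 so that d of at least 0.2 is a planning benchmark read together with its interval, and not by itself evidence of target engagement or benefit.

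The cost is a few sentences in Sections 4 and 13. The EPDS and GSE need no new data. PMS may need an added assessment if the table is right as it stands. The downside is that the conclusion available for H1 and H2 becomes less favourable.
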